7.5 Corneal staining according to Oxford grading scheme

The Oxford 0-5 grading scheme assesses the staining of the corneal area.

The CFS score (ranging from 0 to 5) will be calculated and frequency distribution will be presented at screening, baseline (Day 1), Week 6 and Week 12, for the worse eye and for the contralateral eye. Comparison of the CFS score between treatment groups will be performed at Week 6 and at Week 12 using a CMH test with modified ridit scores stratified by country, separately for the worse eye and for the contralateral eye.

7.6 Far best corrected visual acuity

Far best corrected visual acuity in LogMar will be summarised at screening, baseline (Day 1) and Week 12 using usual descriptive statistics for continuous variable, for the worse eye and for the contralateral eye.

Frequency distribution in classes (*i.e.*, values from 1/10 to 10/10, including NA category, with non-integer numbers rounded to the nearest integer) will also be presented.

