1.3.3 Safety endpoints

Safety and tolerability endpoints are:

- Conjunctival hyperaemia on McMonnies scale in each eye at Week 6 and Week 12
- Change from baseline of conjunctival hyperaemia on McMonnies scale in three classes (improvement, no change, worsening) at Week 6 and Week 12
- Score of each ocular symptom throughout the day and the sum of these scores
- Score of each ocular symptom upon instillation and the sum of these scores
- Score of each ocular sign
- Corneal fluorescein staining (CFS) on Oxford scale
- Far Best Corrected Visual Acuity expressed in LogMar
- Ocular tolerance assessed by the investigator
- Ocular tolerance assessed by the patient
- Ocular and systemic adverse events (AEs) by System Organ Class (SOC) and Preferred Term (PT)

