3 GENERAL CONSIDERATIONS FOR DATA ANALYSES

Statistical analyses will be performed by the Biostatistics unit of AIXIAL. Analyses will be conducted with SAS® software, version 9.4 (SAS Institute, North Caroline, USA).

Continuous data will be described in summary tables presenting, for each treatment group (and for the overall population for baseline descriptions), the number of non-missing observations (n), mean, standard deviation (SD), median, lower quartile (Q1), upper quartile (Q3), minimum and maximum, and 95% CI of the mean/median.

Categorical data will be described in summary tables presenting, for each treatment group (and for the overall population for baseline descriptions), the number of non-missing observations (n), count and percentage of each modality, and 95% CI.

95% CI of a proportion will be calculated using the scoring method of Wilson without continuity correction:

$$\text{Lower Limit} = \frac{2np + z^2 - z\sqrt{z^2 + 4npq}}{2(n + z^2)} \quad \text{Upper Limit} = \frac{2np + z^2 + z\sqrt{z^2 + 4npq}}{2(n + z^2)}$$

with n = number of non-missing observations

 p = percentage

 q = 1 - p

 z = 1.96 for two-sided 95%CI

Except for minimum and maximum, descriptive statistics will be presented with one more decimal than the recorded value.

For all variables, the number of missing values will also be reported in the tables, but they will not be counted for the percentage calculation (categorical data).

Variables recorded for each eye will be described separately for the worse eye and for the other eye (if applicable).

An eye is eligible if inclusion and exclusion (ophthalmological criteria) are respected at screening visit and baseline.

The worse eye is defined as the eligible eye with the highest IOP at baseline at 08:00. In case of no IOP difference between both eyes, the right eye will be considered the worse eye.

Quantitative parameters will be compared between groups using Mixed Model for Repeated Measures (MMRM) or Analysis of Covariance (ANCOVA) model. Assumptions underlying the MMRM (respectively ANCOVA for the sensitivity analyses) will be checked:

- A histogram of residuals will be plotted to check the assumption of normality
- The underlying assumptions of normality of residuals for mixed model will also be checked by using Skewness and Kurtosis statistics
- Normal probability plot and QQ-plot will be performed to check the assumption of normality

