4.3.16 Far best corrected visual acuity

Far best corrected visual acuity will be calculated in Log Mar as: $\text{Log}_{10} (10 / \text{Visual acuity})$ with Visual acuity expressed in /10 unit.

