95% CI (Grade 3)	[xx.x%;xx.x%]	[xx.x%;xx.x%]	
Grade 4	xx (xx.x%)	xx (xx.x%)	
95% CI (Grade 4)	[xx.x%;xx.x%]	[xx.x%;xx.x%]	
Grade 5	xx (xx.x%)	xx (xx.x%)	
95% CI (Grade 5)	[xx.x%;xx.x%]	[xx.x%;xx.x%]	
Missing data	xx (xx.x%)	xx (xx.x%)	
(CMH) Cochran Mantel Haenszel test with modified ridit scores			

(*) Screening / Baseline – Day 1 / Week 6 / Week 12

(**) p-value for Week 6 and Week 12

Name of SAS program: B:\THEA\LT4032-301\Analyse\Pgm\nom_du_programme.sas

Date and time program was run: JJMMYY HH:MM

Study: LT4032-301
Population: Safety set

Page X / N

Table 5.14 – Corneal staining according to Oxford grading scheme – Contralateral eye – Safety set
Same as Table 5.13

Name of SAS program: B:\THEA\LT4032-301\Analyse\Pgm\nom_du_programme.sas

Date and time program was run: JJMMYY HH:MM

Study: LT4032-301
Population: Safety set

Page X / N

Table 5.15 – Far best corrected visual acuity – Worse eye – Safety set

	T4032 (N=XX)	Lumigan (N=XX)
(*) (LogMar)		
n	xx	xx
Mean (SD)	xx.x (xx.x)	xx.x (xx.x)
95% CI (mean)	[xx.x%;xx.x%]	[xx.x%;xx.x%]
Median	xx.x	xx.x
Q1 ; Q3	xx.x	xx.x
Min. ; Max.	xx ; xx	xx ; xx
Missing data	xx	xx
(*) (in classes)		
n	xx	xx
1/10	xx (xx.x%)	xx (xx.x%)
95% CI (1/10)	[xx.x%;xx.x%]	[xx.x%;xx.x%]
...	xx (xx.x%)	xx (xx.x%)
10/10	xx (xx.x%)	xx (xx.x%)
95% CI (10/10)	[xx.x%;xx.x%]	[xx.x%;xx.x%]
NA	xx (xx.x%)	xx (xx.x%)
95% CI (NA)	[xx.x%;xx.x%]	[xx.x%;xx.x%]
Missing data	xx	xx

(*) Screening / Baseline – Day 1 / Week 12

Name of SAS program: B:\THEA\LT4032-301\Analyse\Pgm\nom_du_programme.sas
Date and time program was run: JJMMYY YYYY HH:MM

Study: LT4032-301
Population: Safety set

Page X / N

Table 5.16 – Far best corrected visual acuity – Contralateral eye – Safety set
Same as Table 5.15

Name of SAS program: B:\THEA\LT4032-301\Analyse\Pgm\nom_du_programme.sas
Date and time program was run: JJMMYY YYYY HH:MM

Study: LT4032-301
Population: Azopt Safety Set

Page X / N

Table 5.17 – Azopt Ocular tolerance by the investigator – Azopt Safety Set

	Total (N=XX)
Global judgment of the Azopt ocular tolerance	
n	xx
Very satisfactory	xx (xx.x%)
95% CI (Very satisfactory)	[xx.x%;xx.x%]
Satisfactory	xx (xx.x%)
95% CI (Satisfactory)	[xx.x%;xx.x%]
Not very satisfactory	xx (xx.x%)
95% CI (Not very satisfactory)	[xx.x%;xx.x%]
Unsatisfactory	xx (xx.x%)
95% CI (Unsatisfactory)	[xx.x%;xx.x%]
Missing data	xx
Global judgment of the Azopt ocular tolerance (grouping)	
n	xx
Very satisfactory + Satisfactory	xx (xx.x%)

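### The acuity tables plan no within-eye change and no count by arm of eyes losing a set amount, so individual losses are diluted or can cancel

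*SAP*

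**What the plan says.** SAP Section 1.3.3 lists "Far Best Corrected Visual Acuity expressed in LogMar" among the safety endpoints, as does the protocol synopsis. Section 7.6 then plans, separately for the worse and the contralateral eye: "Far best corrected visual acuity in LogMar will be summarised at screening, baseline (Day 1) and Week 12 using usual descriptive statistics". It adds a frequency table with classes described as "values from 1/10 to 10/10, including NA category, with non-integer numbers rounded to the nearest integer".

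Section 3 says what the usual statistics are: "the number of non-missing observations (n), mean, standard deviation (SD), median, lower quartile (Q1), upper quartile (Q3), minimum and maximum", together with a 95% CI. It also sets the printed precision: "Except for minimum and maximum, descriptive statistics will be presented with one more decimal than the recorded value". Section 4.3.16 derives LogMAR as log10(10/VA), "with Visual acuity expressed in /10 unit".

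The Appendix 2 shell "Table 5.15 – Far best corrected visual acuity – Worse eye – Safety set" has one LogMAR block and one class block, by arm, for screening, Day 1 and Week 12. It has no change row, no shift table, no count of eyes that lost acuity and no p-value column. Table 5.16 repeats it for the contralateral eye. Section 4.3.10 defines change from baseline as the visit value minus the baseline value. Sections 7.1 (hyperaemia) and 7.2 (symptom total) use that definition; Section 7.6 does not.

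**The concern.** A loss of acuity happens in a particular eye. To see it, Week 12 has to be compared with Day 1 in that eye. The plan instead describes the whole arm at Day 1 and the whole arm at Week 12, and leaves the reader to compare two marginal distributions. A few losses hardly move a mean over more than two hundred eyes, and eyes that improve can hide eyes that worsen.

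The point at stake is whether the acuity tables can tell an arm in which some eyes lost vision from an arm in which none did. The primary non-inferiority conclusion is not affected.

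**Working it through.** The plan gives no planning figure for acuity. The one figure that can be reproduced is the conversion. Section 4.3.16 gives log10(10/2) = 0.699 for an acuity of 2/10, which agrees with the 0.7 LogMAR limit in protocol exclusion 2.1.6.

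**Inputs.** SAP Section 1.5 gives 485 randomised and Section 1.4.2.1 gives 1:1 allocation, so about 485/2 ≈ 242 per arm. The Safety set may be slightly smaller. The planned 180 per arm serves as the lower case. The numbers of eyes and sizes of loss below are illustrative assumptions.

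**1. Dilution in the mean.** Shift in arm mean = (eyes losing × loss) / n.

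| Eyes losing | Loss (LogMAR) | n = 242 | n = 180 |
|---|---|---|---|
| 2 | 0.3 | 0.0025 | 0.0033 |
| 10 | 0.2 | 0.008 | 0.011 |
| 12 | 0.3 | 0.015 | 0.020 |

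In reverse, moving the mean by 0.05 through losses of 0.3 needs 0.05/0.3 = 16.7% of eyes, which is 41 of 242 or 30 of 180.

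**2. Cancellation.** Take an arm of 242 in which 12 eyes go from 10/10 to 5/10 (a loss of 0.301), 12 go from 5/10 to 10/10, and the rest do not change. The set of acuity values is the same at Day 1 and Week 12. So the mean, SD, median, quartiles, minimum, maximum and every class count are identical at the two visits, to any number of decimals. The paired data differ plainly: 12 eyes lost 0.301, the changes run from −0.301 to +0.301, and their SD is 0.301 × √(24/241) = 0.095. The mean change is still zero. The SD, the extremes and the loss count carry the information, which is why the fix needs more than a mean change.

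**3. The extremes.** Exclusion 2.1.6 admits eyes up to just under 0.7 LogMAR. An eye that falls from 0.0 to 0.5 therefore need not alter the arm maximum.

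**4. The class table.** Class k covers acuities from k − 0.5 to k + 0.5 tenths, so its width is log10((k + 0.5)/(k − 0.5)). That is 0.146 for 3/10, 0.087 for 5/10 and 0.048 for 9/10; only 2/10 (0.222) and 1/10 (0.477) exceed 0.2. From 10/10, a loss of 0.2 leads to 6.3/10, which rounds to 6/10. So a 0.2 loss starting anywhere from 3/10 to 10/10 changes class. If gains do not offset them, such losses do show in the counts by arm.

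**5. What a loss count would add.** Suppose 12 of 242 eyes (5.0%) in one arm and 2 of 242 (0.8%) in the other lose 0.3 LogMAR. A count shows this directly (Fisher p = 0.012, for illustration only), while the mean in the affected arm moves by 0.015.

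**The case against.** Much can be said for the plan as written, and most of it stands.

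- A reader might infer that only means are given. That is not so: Section 3 adds SD, CI, median, quartiles, minimum and maximum, and Section 7.6 adds the class table.
- A reader might infer from the xx.x in Table 5.15 that precision is fixed at 0.1 LogMAR. The shell uses that placeholder throughout, and the Section 3 rule may give more decimals. At most, text and shell need aligning.
- A reader might infer that rounding to tenths hides losses. Step 4 shows that it does not from the usual starting classes, and exclusion 2.1.6 removes nearly all eyes that would start in the two wide ones.
- A reader might infer that losses cannot be seen in any comparison of arms. Uncompensated losses shift the class counts. A loss reported as an ocular adverse event enters the by-arm tables of Section 7.10.2. Individual data go to listing 16.4. The text at hand has no rule that makes an acuity drop an adverse event, but the protocol is available only as a synopsis, so such a rule cannot be excluded.
- Change from baseline is not used everywhere. Ocular signs (Section 7.4) and corneal staining (Section 7.5) are also given by visit, and the acuity endpoint is named as a value, not as a change.

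What the objection does not supply is a paired summary. None of the planned acuity statistics survives the offsetting in step 2. The documents give no reason to expect exact offsetting, but they do not exclude partial offsetting.

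**Conclusion.** The concern holds in a limited form. Section 7.6 and Tables 5.15 and 5.16 plan no within-eye change and no proportion of eyes losing a set amount by arm. Individual losses are diluted in the mean (0.008 LogMAR for ten eyes losing 0.2 among 242) and can be cancelled by gains in the visit-level statistics and class counts. Apart from the acuity tables, a by-arm signal depends on the loss being reported as an ocular adverse event.

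The missing pairing is the cause; decimals and rounding are not. The sizes rest on about 242 patients per arm and on assumed numbers and sizes of loss. This is a cheap improvement to a descriptive safety summary and not an error that threatens the trial's conclusions.

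**What to change.** In Section 7.6 and Tables 5.15 and 5.16 add, by arm and by eye:

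- the change in LogMAR from Day 1 to Week 12 as defined in Section 4.3.10 (n, mean, SD, median, minimum, maximum, all to two decimals), with a note that a positive change is a loss;
- the number (%) of eyes with a loss of at least a cut-off fixed before unmasking. A value such as 0.2 LogMAR would serve. It is an analysis assumption with no source in the documents, and the sponsor may set another.

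State also how values outside the formula are handled. A measured acuity too low for log10(10/VA), such as a value of 0, counts as a loss. Acuity that was not measured stays missing, for example when the discontinuation visit was by phone, as Section 4.2 allows. Section 7.6 does not define its NA class, so a non-numeric entry should not count as a loss without this distinction.

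The data are already collected and no test is added. The cost is a few more descriptive rows in each table.

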7.7 Automated visual field and Funduscopy

Visual field and the funduscopy at Week 12 will be listed also including screening results and IOP values at each visit (Section 16.2).

7.8 Ocular tolerance by the investigator

Ocular tolerance by the investigator will be assessed on a 4-point ordinal scale (Very satisfactory/Satisfactory/Not very satisfactory/Unsatisfactory).

Assessment of Azopt® ocular tolerance by the investigator at Visit 2 will be presented by frequency distribution for each modality and frequency distribution after regrouping 'very satisfactory' with 'satisfactory', and 'not very satisfactory' with 'unsatisfactory', on Azopt® Safety set, overall.

Assessment of LT4032 or Lumigan® ocular tolerance by the investigator will be presented by frequency distribution for each modality and frequency distribution after regrouping 'very satisfactory' with 'satisfactory', and 'not very satisfactory' with 'unsatisfactory'. After regrouping in 2 classes, comparison of treatment groups at Week 6 and Week 12 will be performed using a CMH stratified by country.

7.9 Ocular tolerance by the patient

Ocular tolerance by the patient will be assessed on a 4-point ordinal scale (Very satisfactory/Satisfactory/Not very satisfactory/Unsatisfactory).

Assessment of Azopt® ocular tolerance at Visit 2 by the patient will be presented by frequency distribution for each modality and frequency distribution after regrouping 'very satisfactory' with 'satisfactory', and 'not very satisfactory' with 'unsatisfactory', on Azopt® Safety set, overall.

Assessment of LT4032 or Lumigan® ocular tolerance by the patient will be presented by frequency distribution for each modality and frequency distribution after regrouping 'very satisfactory' with 'satisfactory', and 'not very satisfactory' with 'unsatisfactory'. After regrouping in 2 classes, comparison of treatment groups at Week 6 and Week 12 will be performed using a CMH stratified.

7.10 Ocular and systemic adverse events

All AEs reported during the study will be coded with MedDRA version the most recent possible at the database lock.

Ocular and systemic AEs will be analysed separately on the basis of the localisation as recorded by the investigator in the CRF.

Summary tables will be produced for treatment-emergent AEs (TEAEs).

TEAEs for Azopt® are AEs that occurred the same day or after the first Azopt® instillation and until the day of the first IMP (LT4032 or Lumigan®).

TEAEs for LT4032 or Lumigan® are AEs that occurred the same day or after the first IMP (LT4032 or Lumigan®) instillation and before or the day of the maximal date between last IMP instillation and Visit 4 (Week 12).

AEs that occurred the day of the first Azopt® instillation will be reviewed during a blind review meeting to decide if they have to be considered as a TEAE for Azopt® or not. AEs that occurred the day of the first IMP instillation will be reviewed during a blind review meeting to decide if they have to be considered as a TEAE for LT4032 or Lumigan® or a TEAE for Azopt®.

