4.3.17 AE time to occurrence

Time to occurrence (days) of an AE will be calculated as follows: Date of onset – Date of IMP first instillation.

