7.10.1 Summary of TEAEs

Separate summaries of treatment-emergent ocular and systemic AEs will be produced by treatment group presenting the number and percentages of patients experiencing at least one:

- AE,
- SAE,
- IMP-related AE (*i.e.*, related or missing relationship with the IMP),
- AE leading to premature study IMP withdrawal.

This table will be presented overall on the Azopt® safety set for TEAE for Azopt® and by treatment group on the Safety set for TEAE for LT4032 or Lumigan®

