7.10.2 Details of AEs

Separate descriptions of treatment-emergent ocular and systemic AEs for Azopt® will be produced overall on Azopt® Safety set:

- Number and percentage of patients experiencing at least one TEAE, as well as the number of TEAEs, by SOC and PT. The same summary table will be produced for SAEs (if any), and AEs related to Azopt® and AEs leading to premature IMP drug withdrawal

Separate descriptions of treatment-emergent ocular and systemic AEs for LT4032 or Lumigan® will be produced by treatment group on the Safety set.

- Number and percentage of patients experiencing at least one TEAEs as well as the number of TEAEs by SOC and PT. The same summary table will be produced for SAEs, IMP-related AEs, IMP-related SAEs and AEs leading to premature IMP drug withdrawal
- Number and percentage of patients experiencing at least one TEAEs as well as the number of TEAEs by SOC, PT and severity
- Number and percentage of patients experiencing at least one TEAEs as well as the number of TEAEs by SOC, PT and relationship with IMP
- Number and percentage of patients with TEAEs by SOC, PT and maximal severity
- Number of patients with TEAEs by SOC, PT and strongest relationship

Summary of treatment-emergent non serious AEs (ocular or systemic) will be produced by treatment group, for LT4032 or Lumigan® presenting the number and percentages of patients experiencing:

- at least one non serious AE
- at least one non serious AE when percentages by PT is $\geq 5\%$ for one group,

as well as the number of these TEAEs by SOC and PT

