7.10.3 Individual listing of AEs

Patient data listings of AEs (ocular and systemic together) will be produced:

- for non emergent AEs on enrolled patients
- for TEAE, serious TEAE, drug related TEAE and TEAE leading to premature IMP drug withdrawal, separately TEAE for Azopt and TEAE for T4032 or Lumigan®
- for Post-treatment AE, ie. after the day of the maximal date between last IMP instillation and Visit 4 (Week 12)

Patient data listings of COVID-19 AEs (PT: COVID-19, Coronavirus infection) will also be produced.

The following variables will be presented:

- Treatment group
- Patient's identifier
- Worse eye (Right Eye/Left eye)
- Gender
- Age at baseline (Day 1)
- Diagnosis (Verbatim)
- SOC
- PT
- Localisation
- Date / time of occurrence
- Time to occurrence (days) from the date of the first IMP instillation
- Date / time of recovery/date of death, if any
- Duration (days)
- Outcome

- Frequency and details
- Severity
- Action taken regarding the IMP
- Requirement for therapy adjustment/modification
- Requirement for surgical/medical procedure,
- Seriousness,
- Relationship with T4032/Lumigan® in the investigator's opinion,
- Relationship with Azopt® in the investigator's opinion,
- Relationship with protocol procedure.

Listings will be sorted by treatment group, patient's identifier and date of onset.

Listing of Deaths, Other Serious adverse events, discontinuations due to adverse events and other adverse events of special interest will be also provided for narratives.

Discontinuations due to adverse events include drug related AE leading to premature IMP drug OR study withdrawal (ie drug related AE with action taken = drug withdrawn OR End of study with premature discontinuation due to this AE).

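### Because SAP 7.10 allocates by onset date, a run-in AE kept as one record that later leads to withdrawal of, is judged related to, or worsens on the randomised drug is missing from the by-arm AE tables

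*SAP*

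**What the plan says.** SAP 7.10 sets two windows. For the run-in product: "TEAEs for Azopt® are AEs that occurred the same day or after the first Azopt® instillation and until the day of the first IMP". For the randomised products: "TEAEs for LT4032 or Lumigan® are AEs that occurred the same day or after the first IMP (LT4032 or Lumigan®) instillation", closing at the later of the last instillation and Visit 4. Section 4.3.17 shows that occurrence is dated from onset: "Time to occurrence (days) of an AE will be calculated as follows: Date of onset – Date of IMP first instillation". Neither definition refers to a later change in severity or seriousness, to causality, or to action taken.

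The one route by which an event can be moved between products is "AEs that occurred the day of the first IMP instillation will be reviewed during a blind review meeting". A parallel review of events on the first Azopt day decides only whether they count as Azopt-emergent at all.

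The two groups of events are displayed differently. For the overview, 7.10.1 says "This table will be presented overall on the Azopt® safety set for TEAE for Azopt® and by treatment group on the Safety set". For the SOC/PT tables, 7.10.2 says "Separate descriptions of treatment-emergent ocular and systemic AEs for Azopt® will be produced overall on Azopt® Safety set"; these include serious events, events related to Azopt, and events leading to withdrawal. The by-arm tables (5.22, 5.27 to 5.37, 5.39 and 5.44 to 5.56) take only events emergent on T4032/Lumigan.

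The listings in 7.10.3 carry severity, seriousness, action taken, relationship with Azopt and, separately, "Relationship with T4032/Lumigan® in the investigator's opinion".

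**The concern.** Every randomised patient is scheduled for 5 weeks on a preserved drop twice daily, then a wash-out, before Day 1. The protocol's ophthalmic exclusions remove only the severe grades of hyperaemia, keratitis and blepharitis. Some patients could therefore enter randomised treatment with a milder ocular event still open. If that event then worsens, is attributed to the new product, or ends it, the date rule credits it to Azopt.

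Safety is a secondary objective, and the comparison is between an unpreserved and a preserved product. An already irritated eye that gets worse is one place where the two could differ. At stake is whether the by-arm tables of TEAEs, SAEs, severity, IMP-related events and events leading to IMP withdrawal are complete. The primary endpoint is not affected.

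**Working it through.** The plan has no figure to reproduce on this point. The check applies the 7.10 rule to test cases.

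Inputs: first Azopt instillation at Day -49 (current screening visit day), first T4032/Lumigan instillation at Day 1, end of window at Day 84 (Week 12).

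Rule: an event is Azopt-emergent if its onset lies from Day -49 to Day 1, and T4032/Lumigan-emergent if its onset lies from Day 1 to Day 84.

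- Onset Day -20, same record worsens on Day 30: Azopt, pooled, only.
- Onset Day -20, randomised drug withdrawn on Day 40: Azopt, pooled, only.
- Onset Day -5 (wash-out), worsens later: Azopt, pooled, only.
- Onset Day 1: in both windows, so settled at blind review.
- Onset Day 2: T4032/Lumigan, by arm.
- Worsening entered as a new event with onset Day 30: T4032/Lumigan, by arm.

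The first three cases are in no by-arm AE table, and the blind review cannot reach them because their onset is not on a first-instillation day.

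Relatedness leaves a further gap. The Azopt SOC/PT table in 7.10.2 counts events related to Azopt, and the by-arm IMP-related table counts only T4032/Lumigan-emergent events. A run-in event later judged related only to T4032/Lumigan meets neither condition and is in neither product's related-event table.

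Withdrawal is similar. The Azopt tables have their own category for events leading to IMP withdrawal, and SAP Section 8 calls Azopt an IMP. A withdrawal of T4032 or Lumigan could therefore be read as a withdrawal of Azopt.

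Scale of one event: 485 randomised / 2 = 242.5 per arm, and 1 / 242.5 = 0.41%, so about 0.4 percentage points of an arm. This assumes an even split and that nearly all randomised patients are in the Safety set.

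**The case against.** The strongest reply is that the gap depends on how sites record worsening. The SAP rests on the full protocol, its addendum and the e-CRF; only the protocol synopsis is available here, and it states no recording convention. If a worsening is entered as a new event, the existing rule already counts it by arm. This stands, and limits the worsening part of the point to events kept as one record. It does not answer the withdrawal and relatedness parts, which need no change in severity.

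A second reply is that the information survives elsewhere. Listings show group, severity, action taken and relationship. Table 1.25 counts discontinuations for adverse events by arm, whatever the onset date. Hyperaemia, daily symptoms, ocular signs and corneal staining are compared by arm at Weeks 6 and 12 (SAP 7.1, 7.2, 7.4, 7.5). This also stands. A reader might infer that the plan hides a difference between the products or understates withdrawals throughout. The documents do not support that. What is lost is the by-arm SOC/PT, severity and causality breakdown of these events; the scores do not capture seriousness, causality or systemic events.

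A third reply concerns the remedy. The listed AE variables show one severity per event and no date of severity change, so worsening cannot be derived from a single record. Also, 7.10.1 treats a missing relationship as related, so a loose relatedness clause would bring in unchanged run-in events. Both objections are right, and the fix allows for them.

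**Conclusion.** The point holds as a modest gap in the by-arm safety tables. On the SAP's wording, a single-record event with onset before the first T4032/Lumigan dose cannot enter those tables, whatever happens to it afterwards. The conclusion rests on reading *occurred* as onset, which 4.3.17 supports, and, for worsening, on the event not being re-entered as new.

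Its size cannot be estimated. The documents give no AE rates and no proportion of patients with an event open at Day 1, so any count of missing patients would rest on assumed rates alone. A patient who has another T4032/Lumigan-emergent event may still appear in the same table, so not every such event removes a patient. The change is worth making because it is cheap and makes the arm comparison more complete.

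**What to change.** Amend SAP 7.10 before database lock, so that allocation is settled without knowledge of the arms. Also count as T4032/Lumigan-emergent any event with earlier onset that:

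- (a) leads to withdrawal of T4032/Lumigan, from the action-taken field, with the derivation naming which product was stopped; or
- (b) is explicitly recorded as related to T4032/Lumigan. For onset before the first dose of that product, a missing relationship should not qualify.

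For (c), worsening in severity or becoming serious after the first T4032/Lumigan instillation: count a worsening entered as a new event by its new onset date. Otherwise decide each event ongoing at Day 1 at the planned blind review, because the listed fields hold no date of severity change. The SAP should also cite the site recording convention, if there is one.

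The cost is SAP wording, a derivation for (a) and (b) from fields already listed, and one more item at the blind review. The small downside is that some events will be counted in both the Azopt and the T4032/Lumigan tables, which needs a footnote.
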